[REDACTED]
[REDACTED]
[REDACTED]

Signature of Coordinating Investigator

Date

[name]. med. [name]

Printed Name of Coordinating Investigator

By my signature, I agree to conduct this study according to this protocol and to make no additions or changes without the consent of the sponsor. In addition, I agree that the study will be carried out in accordance with Good Clinical Practice (GCP), with the Declaration of Helsinki and with the laws and regulations of the country in which the study takes place.

III. Synopsis

Title	A phase II study evaluating the efficacy and safety of imetelstat in patients with HR myelodysplastic syndromes or AML failing HMA-based therapy
Short title	IMpress
Indication	AML and MDS patients failing or being refractory to hypomethylating agent (HMA)-based treatment
Phase	II
Study design	Open-label, single-arm multicenter, phase II study
Participating centers	Germany, France, Australia 12 sites (4 Germany, 4 France, 4 Australia)
Number of subjects	■ to end up with ■ evaluable subjects (■ drop-out rate)
Background and hypothesis of the trial	
Imetelstat (GRN163L) is a covalently-lipidated 13-mer thiophosphoramidate oligonucleotide that acts as a potent specific inhibitor of telomerase. Treatment of various cancer cells with Imetelstat in vitro increases their sensitivity to radiation, decreases their clonogenic potential, and results in altered expression of stem-cell related genes.
 
Data from a phase II study as well as cytogenetic and mutational data for lower risk MDS provide an encouraging basis for further investigation of the agent in higher risk MDS and AML patients ineligible for allo-HSCT, constituting entities with an even greater need for new therapeutic options.

Planned interventions	
All patients will receive 2-hour intravenous (IV) infusion with Imetelstat ■ in a ■ cycle (once every ■ days) for at least ■ cycles. After ■ treatment cycles (■ administrations of Imetelstat) response assessment will be performed on all patients. Non-responding patients will discontinue Imetelstat treatment, undergo EOT and enter the follow-up phase of the trial. Patients who are categorized as responders according to the primary endpoint definition and have BM blasts $\geq 5\%$ at the response assessment ■ will continue Imetelstat treatment every ■ days until loss of response/disease progression. Patients who are categorized as responders according to the primary endpoint definition and have BM blasts $< 5\%$ will continue Imetelstat treatment every ■ days until loss of response/disease progression.

Ethical considerations	
There are currently very few licensed drugs in the EU to treat MDS or AML patients having failed or being refractory to treatment with HMAs. Furthermore, allo-HSCT can be offered only to a minority of those patients. Therefore, new treatment options are urgently needed for this patient cohort. Imetelstat, a first-in-class telomerase inhibitor, with its novel mechanism of action, may provide clinical benefit to MDS and AML patients. First clinical trial results suggest an activity in lower risk MDS and good tolerability.

Study objective(s)	
Primary:
 
To assess the efficacy of Imetelstat for the treatment of AML and MDS patients failing or being refractory to hypomethylating agent (HMA)-based treatment
 
Secondary:
 
Safety objective:
 
• Toxicity as measured by NCI CTCAE v5.0 
Efficacy objective:
 
• Overall survival• Progression-free-survival• Duration of response• Best overall response• Quality of Life (EORTC QLQ-C30)
--------------------	---

Study endpoints	
Primary:
 
 Overall response rate assessed after 4 months of treatment 
 Using combined response assessment criteria for MDS and AML based on IWG 2018 criteria (MDS)¹ and the criteria of the European LeukemiaNet (AML)², as defined in Appendix III a), section 16.3. 
Secondary:
 
Safety Measurements
 
 Toxicity as measured by NCI CTCAE v5.0 
Efficacy Measurements
 
 Overall survival 
 defined as the time from the beginning of imetelstat treatment until death or censored at the date of the last follow-up visit. Progression-free-survival 
 defined as the duration of time from time of imetelstat treatment to time of progression or death, whichever occurs first. A subject who has neither progressed nor died will be censored on the date of last follow-up visit. Duration of best overall response 
 measured from the time measurement criteria are met for CR, CRi, PR or SD (whichever is recorded first, defined in Appendix III a), section 16.3) until the first date at which recurrent or progressive disease is objectively documented. Best overall response 
 defined as the best response recorded from the start of the imetelstat treatment until disease progression (taking as reference for progressive disease the smallest measurements recorded since the treatment started). Response based on IWG 2023 criteria (MDS population only) 
 assessed in week [REDACTED] of treatment with imetelstat, for definition see Appendix III b). Scores of EORTC QLQ-C30 (version 3) 
 Global health status / QoL Functional scales Symptom scales / items
-----------------	--

Medical condition	AML and MDS patients failing or being refractory to hypomethylating agent (HMA)-based treatment
Eligibility criteria	
Inclusion criteria:
 
 1 Signed written informed consent 2 Male and female ≥ 18 years at the first screening 3 Must be able to adhere to the study visit schedule and other protocol requirements 4 Initial diagnosis of AML or MDS according to WHO 2016 classification 5 At least one cytopenia (ANC $< \blacksquare/\mu\text{L}$ or platelet count $< \blacksquare/\mu\text{L}$ or hemoglobin $< \blacksquare \text{ g/dL}$) 6 
 a. Failure to achieve complete or partial response or hematological improvement observed after at least six azacitidine monotherapy or four decitabine monotherapy based 4-week treatment cycles administered during the past two years OR b. Failure to achieve complete or partial response or hematological improvement observed after at least two 4-week treatment cycles with azacitidine plus venetoclax or with decitabine plus venetoclax during the past two years OR c. Relapse after initial complete or partial response or hematological improvement observed after at least six (azacitidine) or four (decitabine) based 4-week treatment cycles administered during the past two years OR d. Relapse after initial complete or partial response or hematological improvement observed after at least two 4-week treatment cycles with azacitidine plus venetoclax or with decitabine plus venetoclax during the past two years OR e. Intolerance to treatment with HMA-based therapy during the past two years 7 Not eligible for allogeneic stem cell transplantation 8 $\geq 5\%$ bone marrow blasts at screening 9 Off all other treatments for AML/MDS for at least 14 days; G-CSF and erythropoietin are allowed before and during the study as clinically indicated 10 ECOG performance status of 0-2 11 Biochemical laboratory test values must be within the following limits: 

 

 

	
[REDACTED]
 
[REDACTED]
 
[REDACTED]

12	Availability of blood counts and transfusion events for previous 16 weeks
13	
Women of childbearing potential and practicing a highly effective method of birth control according to the Clinical Trial Facilitation Coordination Group Recommendation (Version 1.1, 2020)²⁸:
 
 - combined (estrogen and progestogen containing) hormonal contraception associated with inhibition of ovulation: 
 o oral o intravaginal o transdermal - progestogen-only hormonal contraception associated with inhibition of ovulation: 
 o oral o injectable o implantable - intrauterine device (IUD) - intrauterine hormone-releasing system (IUS) - bilateral tubal occlusion - vasectomised partner - sexual abstinence 
For females, these restrictions apply for 3 months after the end of dosing. Note: If the childbearing potential changes after start of the study (e.g., woman who is not heterosexually active becomes active, premenarchal woman experiences menarche) a woman must begin a highly effective method of birth control, as described above

14	A woman of childbearing potential must have a negative serum (β -human chorionic gonadotropin [β -hCG] pregnancy test at screening and agree to be tested (serum or urine) on day 1 of every cycle and at EOT
15	A man who is sexually active with a woman of childbearing potential and has not had a vasectomy must agree to use a barrier method of birth control eg, either condom with spermicidal foam/gel/film/cream/suppository or partner with occlusive cap (diaphragm or cervical/vault caps) with spermicidal foam/gel/film/cream/suppository, and all men must also not donate sperm during the study. For males, these restrictions apply for 3 months after the end of dosing
16	France-specific inclusion criterion: Subjects participating at French sites must be covered by the French public welfare system.
17	Patients who are relapsed or refractory to, or not eligible for, therapy with approved and available FLT3 or IDH1/IDH2 inhibitors or other approved targeted therapies.

Eligibility criteria	Exclusion criteria
	
 1 Chemotherapy within the 14 days prior to the first dose of imetelstat being administered (other than hydroxyurea) 2 Subject has known allergies, hypersensitivity, or intolerance to imetelstat or its excipients (refer to the IB) 3 Subject has received an experimental or investigational drug or used an invasive investigational medical device within 30 days prior to day 1 of C1 4 Prior treatment with imetelstat 5 Prior history of intensive chemotherapy or hematopoietic stem cell transplant 6 Major surgery within 4 weeks prior to day 1 of C1 (excluding the placement of vascular access and other minor surgical procedures) 7 Diagnosed or treated for malignancy other than MDS or AML, except: 
 a. Malignancy treated with curative intent and with no known active disease present for 3 years before day 1 of C1 b. Adequately treated non-melanoma skin cancer or lentigo maligna without evidence of disease c. Adequately treated cervical carcinoma in situ without evidence of disease 8 Clinically significant cardiovascular disease such as uncontrolled or symptomatic arrhythmias, congestive heart failure, or myocardial infarction within 6 months of day 1 of C1, or any Class 3 (moderate) or Class 4 (severe) cardiac disease as defined by the New York Heart Association Functional Classification 9 Known history of human immunodeficiency virus (HIV) or any uncontrolled active systemic infection requiring IV antibiotics 10 Active systemic hepatitis infection requiring treatment (carriers of hepatitis virus are permitted to enter the study), or known acute or chronic liver disease including cirrhosis 11 Any life-threatening illness, medical condition, or organ system dysfunction which, in the investigator's opinion, could compromise the subject's safety, interfere with the imetelstat metabolism, or put the study outcomes at undue risk; Subject has any condition for which, in the opinion of the investigator, participation would not be in the best interest of the subject (eg, compromise the well-being) or that could prevent, limit, or confound the protocol-specified assessments 12 Females who are pregnant or are currently breastfeeding or planning to become pregnant while enrolled in this study or within 3 months after the end of dosing 13 Subject is a man who plans to father a child while enrolled in this study or within 3 months after the end of dosing 14 Subject is in custody by order of an authority or a court of law 15 Previous assignment to treatment during this study

	
16 Close affiliation with the investigator (e.g., a close relative) or persons working at the study site
 
17 Subject is an employee of the sponsor or involved CRO
 
18 Criteria which in the opinion of the investigator preclude participation for scientific reasons, for reasons of compliance, or for reasons of the subject's safety

Study treatment(s)	
Test drug: Imetelstat sodium
 
Starting dose: [REDACTED]
 
Dosing regimen: [REDACTED] until disease progression, unacceptable toxicity, withdrawal of consent, or lack of response. Responding patients at cycle [REDACTED] (defined as CR [complete remission], CRi [CR with incomplete hematologic recovery] or PR [partial remission] and/or showing a hematologic improvement for one or several lines) are eligible to continue treatment. Responding patients who have BM blasts $\geq 5\%$ at the response assessment [REDACTED] will continue Imetelstat treatment every [REDACTED] days until loss of response/disease progression. Responding patients who have BM blasts $< 5\%$ will continue Imetelstat treatment every [REDACTED] days until loss of response/disease progression. Non-responding patients will discontinue Imetelstat treatment, undergo EOT and enter the follow-up phase of the trial.
 
Administration route: Intravenous (IV)

ALT	Alanine aminotransferase
AML	Acute myeloid leukemia
ANC	Absolute Neutrophil Count
AST	Aspartate aminotransferase
ATC	Anatomical Therapeutic Chemical
AUS	Australia
AZA	5-azacytidine
β-HCG	Beta human chorionic gonadotropin
BM	Bone marrow
BMI	Body Mass Index
BSC	Best supportive care
C1D1	Cycle 1 Day 1
CBC	Complete blood count
CI	Confidence Interval
CPI	Coordinating Principal Investigator (Leiter der klinischen Prüfung)
CR	Complete Remission
CRi	Complete Remission with Incomplete hematologic recovery
CRO	Contract Research Organization
CTCAE	Common Terminology Criteria for Adverse Events
DDI	Drug-Drug Interaction
DLT	Dose Limiting Toxicity
DM	Data Manager
DMP	Data Management Plan
DMC	Data monitoring committee
DSUR	Development Safety Update Report
DVP	Data Validation Plan
EC	Ethics committee
ECG	Electrocardiogram
ECOG PS	Eastern Cooperative Oncology Group Performance Status

eCRF	Electronic case report form
EOS	End of Study
EOT	End of Treatment
ESA	Erythropoiesis-stimulating agents
EU	European Union
FAS	Full analysis set
FCBP	Female of childbearing potential
FU	Follow-up
GCP	Good clinical practice
G-CSF	Granulocyte colony-stimulating factor
Hb	Hemoglobin
HI	Hematologic Improvement
HI-E	Hematological improvement - erythroid
HI-N	Hematological improvement - neutrophils
HI-P	Hematological improvement - platelets
HMA	Hypomethylating agents
HR MDS	Higher Risk Myelodysplastic syndromes
HSCs	Hematopoietic stem cells
hTERT	human Telomerase Reverse Transcriptase
hTR	human Telomerase Ribonucleic acid template
IB	Investigators Brochure
ICF	Informed consent form
ICMJE	International Committee of Medical Journal Editors
ICT	Iron chelation therapy
IEC	Independent ethics committee
IMP	Investigational Medicinal Product
IPSS-R	International Prognostic Scoring System-Revised
ISF	Investigator site file
IWG	International Working Group
LDH	Lactate Dehydrogenase
LEN	Lenalidomide
LFT	Liver function test
MCH	Mean corpuscular hemoglobin
MCHC	Mean corpuscular hemoglobin concentration

MCV	Mean corpuscular volume
MDS	Myelodysplastic syndrome
MDS-RS	MDS with ring-sideroblastic phenotype
MedDRA	Medical Dictionary for Regulatory Activities
MLFS	Morphologic Leukemia-Free State
NCI	National Cancer Institute
NGS	Next Generation Sequencing
nRBC	nucleated Red Blood Cells
OS	Overall survival
ORR	Overall Response Rate
PB	Peripheral blood
PD	Progressive Disease
pEP	primary Endpoint
PFS	Progression-Free Survival
PPS	Per Protocol Set
PR	Partial Remission
pRBCs	Packed red blood cells

⁴ Pregnancy tests for verification of in-/exclusion criteria prior to starting with study medication / inclusion with a minimum sensitivity of 25 mIU/mL for women of child-bearing potential only is to be done not more than 3 days prior to initiation of treatment. In each case of delayed menstrual period (over one month between menstruations) confirmation of absence of pregnancy is required. This requirement also applies to women of childbearing potential with infrequent or irregular menstrual cycles.

⁵ Imetelstat sodium will be administered at a starting dose of ■ mg/kg given intravenously every ■ weeks for the first ■ cycles of treatment.

⁶ Treatment with imetelstat will be continued until results of response assessment are available

⁷ Imetelstat administration at this visit only for responders with ≥5% BM blasts.

LOCAL LABORATORY: Response assessment ⁸						x ⁹				x	
Central assessments / correlative analyses (EU: Leipzig, AUS: QIMRB, Brisbane)											
Bone marrow aspiration (5 mL sodium heparinized in separate tubes for central assessments)	x					x				x	
Peripheral blood sampling for central assessments (10 mL sodium heparinized blood in separate tubes for central assessments)	x					x				x	
Genetic profiling (NGS) at central laboratories	x									x	
MRD analyses at central laboratories						x				x	
Telomere profiling at central laboratories	x										
Telomere length at central laboratories	x									x	
Study-specific biomaterial collection	x					x				x	
Local assessments											
CBC with differential (local)	x					x				x	
PB blast assessment (local)	x			x		x		x		x	
BM cytology assessment (local) ¹⁰	x					x				x	
Serum chemistry (local)	x	x		x		x		x		x	
Automated CBC (local)	x	x	x	x	x	x	x	x	x	x	x
Cytogenetics (local)	x					x				x	

⁸ Response assessment will be performed based on the combined response assessment criteria for MDS and AML based on IWG 2018 criteria (MDS) and the criteria of the European LeukemiaNet (AML) in [REDACTED] after ending [REDACTED] (see Appendix III, section 16.3). Response assessment period lasts until all necessary lab results are available and can be assessed. Meanwhile patients further receive IMP until result of response assessment are present (starting [REDACTED]). Results of response assessment are the basis for further treatment or proceeding to EOT. Additionally, the BM blast levels at each response assessment from cycle 5 will be the basis for deciding the frequency of treatment of imetelstat (every [REDACTED] weeks or every [REDACTED] weeks) until the next response assessment.

⁹ If signs of disease progression are present in bone marrow at the response assessment after 4 doses with imetelstat, treatment with imetelstat must be discontinued and the patient to undergo EOT.

¹⁰ A BM biopsy is to be collected when adequate aspirate is not attainable or if the BM aspirate shows fewer than 5% bone marrow blasts. Whenever a BM sample is collected, both BM and PB smears are to be prepared.

Part 2a – extension treatment phase, from cycle 5 until loss of response / disease progression (**responders with BM blasts <5% only**)

VISIT NO.	■	■	■	■	■	■	■	■	■
Study Day (± 3d)	■	■	■	■	■	■	■	■	■
Study Week	■	■	■	■	■	■	■	■	■
Cycle	■	■	■	■	■	■	■	■	■
Informed consent									
In- / exclusion criteria ³									
MDS/AML related medical history									
Concomitant MDS/AML specific medication	x		x		x		x		x
Physical examination, vitals	x	x ¹¹	x	x ¹¹	x	x ¹¹	x	x	x
ECOG performance status									
BMI			x						
Pregnancy test ⁴	x		x		x		x		x
Imetelstat administration ⁵ and drug account	x		x		x		x ⁶		x ¹²
Toxicity/AE assessment	x	x ¹¹	x	x ¹¹	x	x ¹¹	x	x	x
Quality of life (QoL, EORTC QLQ-C30)	x		x		x		x	x	x
LOCAL LABORATORY: Response assessment ⁸			x					x	x ¹³
Central assessments / correlative analyses (EU: Leipzig, AUS: QIMRB, Brisbane)									
Bone marrow aspiration (5 mL sodium heparinized in separate tubes for central assessments)			x						
Peripheral blood sampling for central assessments (10 mL sodium heparinized blood in separate tubes for central assessments)			x						
Genetic profiling (NGS) at central laboratories									
MRD analyses at central laboratories			x						

¹¹ Can be done at patient's general practitioner practice at investigator's discretion (for non-treatment visits only)

¹² If a patient is responding to imetelstat and continues beyond ■, each disease assessment should determine whether treatment with imetelstat is given every ■ weeks (responding with ≥5% BM blasts) or every ■ weeks (responding with <5% BM blasts).

¹³ Response assessment every 3 months (when BM cytomorphology is carried out)

Telomere length & telomerase profiling at central laboratories									
Study-specific biomaterial collection			x						
Local assessments									
CBC with differential (local)			x					x ¹⁴	x ¹⁵
PB blast assessment (local)	x		x		x		x	x ¹⁴	x ¹⁵
BM cytology assessment (local) ¹⁰			x					x ¹⁴	x ¹⁵
Serum chemistry (local)	x		x		x		x	x	x
Automated CBC (local)	x	x ¹¹	x	x ¹¹	x	x ¹¹	x	x	x
Cytogenetics (local)			x					x	

¹⁴ Only to be carried out if the last assessment is more than 14d apart

¹⁵ BM / CBC assessment every 3 months and at every timepoint of suspected progression starting ■ weeks after last morphology assessment at ■

Part 2b – extension treatment phase, from cycle 5 until loss of response / disease progression (**responders with BM blasts $\geq 5\%$ only**)

VISIT NO.									
Study Day ($\pm 3d$)									
Study Week									
Cycle									
Informed consent									
In- / exclusion criteria ³									
MDS/AML related medical history									
Concomitant MDS/AML specific medication	x		x		x		x		x
Physical examination, vitals	x	x	x	x	x	x	x	x	x
ECOG performance status									
BMI			x						
Pregnancy test ⁴	x		x		x		x		x
Imetelstat administration ⁵ and drug account	x	x	x ⁶	x	x	x	x	x	x ¹²
Toxicity/AE assessment	x	x	x	x	x	x	x	x	x
Quality of life (QoL, EORTC QLQ-C30)	x		x		x		x	x	x
LOCAL LABORATORY: Response assessment ⁸			x					x	x ¹³
Central assessments / correlative analyses (EU: Leipzig, AUS: QIMRB, Brisbane)									
Bone marrow aspiration (5 mL sodium heparinized in separate tubes for central assessments)			x						
Peripheral blood sampling for central assessments (10 mL sodium heparinized blood in separate tubes for central assessments)			x						
Genetic profiling (NGS) at central laboratories									
MRD analyses at central laboratories			x						
Telomere length & telomerase profiling at central laboratories									
Study-specific biomaterial collection			x						
Local assessments									
CBC with differential (local)			x					x ¹⁴	x ¹⁵
PB blast assessment (local)	x		x		x		x	x ¹⁴	x ¹⁵
BM cytology assessment (local) ¹⁰			x					x ¹⁴	x ¹⁵
Serum chemistry (local)	x		x		x		x	x	x
Automated CBC (local)	x	x	x	x	x	x	x	x	x
Cytogenetics (local)			x					x	

Part 2c – extension treatment phase, from cycle 5 (non-responders with stable or controlled disease who continue treatment at the investigator's discretion)

VISIT NO.	██████████
Study Day (± 3d)	████████████████████
Study Week	██████
Cycle	██████████
Concomitant MDS/AML specific medication	X
Pregnancy test	X
Imetelstat administration and drug account	X ¹⁶
Toxicity/AE assessment	X
LOCAL LABORATORY: Response assessment ¹⁷	X ¹⁸
CBC with differential (local)	X ¹⁸
PB blast assessment (local)	X ¹⁸
BM cytology assessment (local)	X ¹⁸

¹⁶ The dosing frequency for imetelstat (every ■ weeks or every ■ weeks) for these subjects will be determined at the discretion of the investigator.

17 Response assessment will be performed based on the combined response assessment criteria for MDS and AML based on IWG 2018 criteria (MDS) and the criteria of the European LeukemiaNet (AML). Additionally, the BM blast level at each response assessment will be the basis for deciding the frequency of treatment of imetelstat (every █ weeks or every █ weeks) until the next response assessment.

¹⁸ Optional response assessment and lab measurements to be done according to standard of care and/or only in case needed to assess and follow-up on (S)AEs and dose modifications

Part 3 – EOT and follow-up period (all patients)

VISIT NO.	██████ ██████ ██████	████ ██████ ██████	██████████ ██████ ██████████ ██████████	██████	██████████
Study Day (± 3d)	██████	██████	██████	██████████	██████████
Study Week	██████	██████	██████	██████	██████
Informed consent					
In- / exclusion criteria ³					
MDS/AML related medical history					
Concomitant MDS/AML specific medication	x	x	x	x	
Physical examination, vitals	x	x	x	x	
BMI	x	x	x	x	
Pregnancy test ⁴	x	x	x	x	
Toxicity/AE assessment	x	x	x	x	
Quality of life (QoL, EORTC QLQ-C30)	x	x	x		
Information on current state of condition / survival status	x	x	x	x	x
Central assessments / correlative analyses (EU: Leipzig, AUS: QIMRB, Brisbane)					
Bone marrow aspiration (5 mL sodium heparinized in separate tubes for central assessments)		x ²²			
Peripheral blood sampling for central assessments (10 mL sodium heparinized blood in separate tubes for central assessments)		x ²²			
Genetic profiling (NGS) at central laboratories		x			
MRD analyses at central laboratories					
Telomere length & telomerase profiling at central laboratories		x			
Study-specific biomaterial collection		x			
Local assessments					
Serum chemistry (local)	x	x	x		
Automated CBC (local)	x	x	x		

¹⁹ FU2/EOS can be carried out on the telephone

²⁰ To be carried out once the results of the response assessment from █████ are available and at the latest 14 days after the date of decision of treatment discontinuation

²¹ Responders after the assessment at █████ will be treated further until loss of response/disease progression. In the case of safety issues, loss of response or disease progression, patients will undergo the EOT visit within 14 days from the date of decision of treatment discontinuation.

²² BM and PB sample collection should only be performed at EOT visit if > 90 days from prior BM procedure

1 Scientific background and rationale

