8.1.5 MDS/AML disease assessment: [REDACTED]

The primary MDS/AML disease assessment according to the combined MDS/AML response criteria (Appendix III a), section 16.3) (primary endpoint assessment) will be performed on samples taken at [REDACTED]. The assessment will be performed by the corresponding investigator.

The disease assessment for the primary endpoint should be completed after four completed cycles with imetelstat (allowing for dose delays). For the disease assessment at least the results of the cytomorphology assessment, automated CBC values and cytogenetic results of visit 9 as well as any information on Hb and transfusions between enrollment and visit 9 are required and must be available prior to / for the disease assessment.

In order for subjects to remain on treatment beyond the first four cycles, the following criteria must be confirmed upon the completion of the disease assessment by the investigator based on the combined response criteria based on IWG 2018 criteria (MDS)¹ and the criteria of the European LeukemiaNet (AML)²:

- **At least partial remission (PR):**
 - This includes CR, CRi, and PR and HI (any line) as per the combined response criteria used in this trial (see Appendix III a))

MLFS will be recorded but is not a criterion for treatment continuation.

Based on the outcome of the disease assessment, subjects will either be discontinued from treatment with IMP and enter the post-treatment follow-up period or continue treatment with IMP in the extension phase of the treatment period.

For subjects that meet the criteria to continue treatment in the extension phase, the duration between the last dose of IMP administered in the primary phase and the first extension phase dose should not be delayed solely due to awaiting cytomorphology/cytogenetics results contingent that the investigator has confirmed absence of signs of disease progression based on review of peripheral blood parameters.

A BM biopsy is to be collected only when adequate aspirate is not attainable or if the BM aspirate shows fewer than 5% bone marrow blasts. Whenever a BM sample is collected, both BM and PB smears are to be prepared. Refer to the Laboratory Manual for additional information.

Further procedures/evaluations to be performed at [REDACTED] are specified in VII Schedule of assessments and procedures, part 1 and in section 8.2 Descriptions of assessments.

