10.9.3 Adverse Events

Adverse events will be defined as treatment-emergent if they are newly occurring or worsen following treatment with imetelstat. For this trial, the only adverse events that will be counted will be TEAEs (see section 9.1.2). TEAEs will be classified by system organ class and preferred term using the Medical Dictionary for Regulatory Activities (MedDRA).

Tables for TEAEs will show the number and frequencies of incidences by severity and relation to IMP. Individual listings of AEs, SAEs and deaths within 30 days from last exposure to IMP will be generated.

TEAEs leading to premature discontinuation of study drug or withdrawal from the study will be summarized and listed in the same manner.

The percentage of patients with unacceptable toxicity acc. to CTCAE v5.0 criteria will be provided for week 4 (C4) and week 17 (beginning of C5, V9), and accompanying exact two-sided 95% confidence interval using the Clopper-Pearson method will be provided.

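### Schedule footnotes give conflicting rules for dosing frequency in Part 2c and, for some patients, for the dose at the visit after visit 9

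*Protocol*

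**What the plan says.** **Part 2c (non-responders with stable or controlled disease who continue from cycle 5).** Three footnotes to one table bear on dosing frequency.

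- Footnote 16: the frequency "for these subjects will be determined at the discretion of the investigator".
- Footnote 17: "the BM blast level at each response assessment will be the basis for deciding the frequency of treatment of imetelstat".
- Footnote 18: the response assessment and the laboratory measurements in this part, including marrow cytology, are optional.

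Protocol 5.1.4 and 7.1 state the blast-level rule for patients who are responding. They do not extend it to non-responders.

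**Visit after visit 9 (last column of Part 1).**

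- Footnote 7, on the dose at this visit: "Imetelstat administration at this visit only for responders with ≥5% BM blasts".
- Footnote 6, on the visit 9 dose: "Treatment with imetelstat will be continued until results of response assessment are available".
- Footnote 8, on the response assessment row: "Response assessment period lasts until all necessary lab results are available and can be assessed". It adds: "Meanwhile patients further receive IMP until result of response assessment are present".
- Protocol 8.1.5 requires the visit 9 cytomorphology, blood count and cytogenetics before response is assessed. For patients who qualify for the extension phase, it says the first extension dose "should not be delayed solely due to awaiting cytomorphology/cytogenetics results", on condition that peripheral blood shows no sign of progression.

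SAP 2.4 repeats all of these footnotes.

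**The concern.** A site cannot apply both footnote 16 and footnote 17 when they point to different frequencies. Nor can it apply both footnote 7 and footnote 8 to a patient whose visit 9 result has not arrived.

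This matters for patients first. Protocol 7.2.2.1 links the frequency and severity of cytopenias to dose intensity, including how often the drug is given, and protocol 1.3.1 says more frequent dosing could aggravate neutropenia.

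It also matters for the data. Protocol 12.3 demands strict adherence and does not let investigators modify procedures. The same dose could therefore be compliant under one footnote and a deviation under another. Exposure and TEAE summaries after visit 9 would then combine patients treated under different rules.

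**Working it through.** The plan gives no figure to reproduce. The check sets the texts side by side, with a little arithmetic on visit timing.

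**Visit timing.** SAP 8.3 places visit 5 at week 9, cycle 3, and visit 9 at week 17, cycle 5. Protocol 10.9.3 agrees on visit 9: "week 17 (beginning of C5, V9".

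- Cycle length: (17 − 9) weeks / (5 − 3) cycles = 4 weeks.
- Visit spacing: (17 − 9) weeks / (9 − 5) visits = 2 weeks, which matches the two-weekly dosing in SAP 2.1.2.
- The visit after visit 9 is therefore nominally 14 days later, in week 19. Cycle 5 covers weeks 17 to 20, so this visit is still in cycle 5.
- Each visit may move by ±3 days (footnote 1). The gap runs from 14 − 6 = 8 days to 14 + 6 = 20 days.

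**Instructions at the visit after visit 9, by patient status.**

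| Status at that visit | Footnote 7 | Other text | Consistent? |
|---|---|---|---|
| Result known, responder, blasts ≥5% | Dose | More frequent schedule continues (5.1.3, 8.1.6) | Yes |
| Result known, responder, blasts <5% | No dose | Less frequent schedule (5.1.3, 8.1.6) | Yes |
| Result known, non-responder who stops | No dose | EOT and follow-up (5.1.3) | Yes |
| Result known, non-responder continuing under Part 2c | No dose | May be treated from cycle 5 at a frequency set under footnote 16 or 17 | No, if that frequency puts a dose here |
| Result pending | No dose, because responder status is not established | Footnotes 6 and 8: continue until the result is available. 8.1.5: do not delay on account of pending results if peripheral blood shows no progression | No |

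Two of the five situations are in conflict. The documents give no laboratory turnaround time, so the number of patients with a result pending at 8 to 20 days can be neither assumed nor excluded.

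**Part 2c.** Footnotes 16 and 17 address the same patients, the same table and the same decision, and no text ranks them. If the optional assessment is not done, footnote 17 has no blast value to work from. If it is done, the investigator's choice and the blast level can disagree.

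The two Part 2c frequencies are redacted. Assume they equal the responder schedules: every 2 weeks (SAP 2.1.2) and every 4 weeks (synopsis time plan, responders with blasts <5%). The dose-intensity ratio is then (4/2) / (4/4) = 2 doses against 1 per four-week cycle, a factor of 2. Where the two rules lead to the same frequency the ratio is 1.

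**The case against.** The case against is strong on scope.

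- **Footnotes 6 and 7 are sequential.** They sit on consecutive visits. Once the visit 9 result is known, they agree for responders and for non-responders who stop. A reader might infer that the schedule gives opposite instructions generally at this visit; the table above does not support that.
- **Footnote 8 does not stand alone.** A reader might infer that everyone is dosed until results arrive. Section 8.1.5 adds a peripheral-blood condition and is worded for patients who qualify for the extension phase. The starting point of footnote 8's waiting clause is also redacted.
- **A withheld dose may only be late.** Protocol 8.1.7 postpones dosing visits when dosing is delayed, so a pending patient later classed as a responder with blasts ≥5% need not lose the dose.
- **The primary endpoint is not touched.** Response is assessed on visit 9 samples (protocol 2.3.1 and 8.1.5), before the disputed dose. SAP 7.3 calls a deviation critical if it might influence the primary analysis, and this dose cannot. SAP 6.2.3 also cuts compliance and total dose at a stated visit, whose number is redacted.
- **Part 2c is set apart.** Protocol 5.1.4 and 8.1.6 say its data may be collected without affecting the primary objectives, timelines or statistical analyses. All analyses are exploratory (protocol 10.1).

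These points narrow the finding and remove any consequence for the response rate. They do not settle which footnote governs Part 2c, or what a site does when a result is pending. The statement that Part 2c leaves the analyses unaffected does not tell a site how often to dose. Nor does SAP 8.5 contain a rule removing Part 2c doses or events from the by-cycle dose-intensity or TEAE summaries.

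**Conclusion.** Wrong as written: this is an internal inconsistency in dosing instructions, not a design choice and not merely missing detail. It should be corrected.

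- **Part 2c is the firmer part.** Every Part 2c patient faces the ambiguity. A reader might infer that every such patient's dose intensity could be halved or doubled. That does not follow: dosing differs only where the investigator's choice departs from the blast rule, and the factor of 2 assumes the redacted frequencies match the responder schedules.
- **The visit after visit 9 is narrower.** The conflict is confined to patients whose visit 9 result is still pending 8 to 20 days later (14 nominally), a number the documents do not allow one to estimate, and to non-responders continuing under Part 2c who would be dosed at that visit. The Part 2c case rests on the table's stated start at cycle 5; its visit and day headers are redacted.

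The visit 9 response rate is unaffected. The consequences are for patient dosing and safety, for what counts as a dosing deviation, and for exposure and TEAE summaries after visit 9.

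**What to change.** 1. Reconcile footnotes 6, 7 and 8 with section 8.1.5 and with Part 2c, so that one instruction covers a patient whose visit 9 response is not yet classified at the next visit, and one covers a non-responder continuing under Part 2c.
2. Reconcile footnotes 16, 17 and 18 with sections 5.1.4 and 7.1, so that one rule sets dosing frequency in Part 2c and it is clear what applies when the optional assessment is not done.
3. Mirror both changes in SAP 2.4.

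The sponsor, with its clinical advisers, decides which instruction stands; this review takes no position on that. The cost is rewording a few footnotes, and the linked sections where needed, in the protocol and SAP. The rewording itself needs no extra visits, assessments or analyses.
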